5.4. Secondary Endpoint(s) Analysis

5.4.1. Key Secondary Endpoint

Similar to the primary analysis, analysis of the key secondary endpoint will be based on the full efficacy analysis set using the MADRS total scores collected during the double-blind phase.

5.4.1.1. Definition

The key secondary efficacy endpoint is the change from baseline in MADRS total score from Day 1 (prerandomization) to Day 2.

5.4.1.2. Key Secondary Estimand

All components as described under Primary Estimand (Section 5.3.2) apply to the Key Secondary Estimand except for the variable and summary measure:

Variable: Change from baseline to Day 2 in the MADRS total score

Summary Measure: Difference in means between each dose and placebo for the change from baseline in MADRS total score at Day 2.

5.4.1.3. Analysis Methods

The key secondary efficacy variable, change from baseline in MADRS total score at Day 2 in the double-blind treatment phase, will be analyzed using the same MMRM model as described for the primary endpoint.

5.5. Other Endpoint(s)

Analyses of other endpoints will be based on the full efficacy analysis set unless otherwise specified.

5.5.1. Response (≥50% Improvement) Based on MADRS Total Score

5.5.1.1. Definition

A participant is defined as a responder at a given time point if the percent improvement from baseline in MADRS is $\geq 50\%$ at that time point (ie, percent change $\leq -50\%$).

5.5.1.2. Analysis

The number and percentage of participants who achieve a response will be summarized at each time point during the double-blind phase by intervention group.

Response rates over time will be plotted for double-blind phase.

5.5.2. Remission (MADRS ≤10) Based on MADRS Total Score

5.5.2.1. Definition

A participant is defined as a remitter at a given time point if the MADRS total score is ≤ 10 at that time point.

5.5.2.2. Analysis

The number and percentage of participants who achieve remission (MADRS \leq 10) will be summarized at each time point during the double-blind phase by intervention group.

Remission rates will be plotted for double-blind phase.

5.5.3. Remission (MADRS ≤12) Based on MADRS Total Score

5.5.3.1. Definition

A participant is defined as a remitter at a given time point if the MADRS total score is ≤ 12 at that time point.

5.5.3.2. Analysis

The number and percentage of participants who achieve remission (MADRS \leq 12) will be summarized at each time point during the double-blind phase by intervention group.

Remission rates will be plotted for double-blind phase.

5.5.4. Clinical Global Impression – Severity (CGI-S)

5.5.4.1. Definition

The CGI-S provides an overall clinician-determined summary measure of the severity of the participant's illness that takes into account all available information, including knowledge of the participant's history, psychosocial circumstances, symptoms, behavior, and the impact of the symptoms on the participant's ability to function. (Guy 1991) The CGI-S evaluates the severity of psychopathology on a scale of 1 to 7. Considering total clinical experience with the depression population, a participant is assessed on severity of illness at the time of rating according to: 0=not assessed; 1=normal (not at all ill); 2=borderline ill; 3=mildly ill; 4=moderately ill; 5=markedly ill; 6=severely ill; 7=among the most extremely ill patients.

A score of 0 indicates that the participant was not assessed, and will be treated as missing. The score from 1 to 7 will be summarized as recorded.

Negative changes in CGI-S score indicate improvement.

5.5.4.2. Analysis

Descriptive statistics of the actual values and the change from baseline will be presented by intervention group for observed case data.

A frequency distribution over time of the CGI-S scores will be provided by intervention group. The frequency distributions will be presented graphically using stacked bar charts for the baseline, Day 2 and Day 28.

5.5.5. Patient Health Questionnaire - 9 Item (PHQ-9)

5.5.5.1. Definition

The 9-item Patient Health Questionnaire - 9 Item (PHQ-9) scale scores each of the 9 symptom domains of the DSM-5 MDD criteria and it has been used both as a screening tool and a measure of response to intervention for depression. Each item is rated on a 4-point scale (0=not at all, 1=several days, 2=more than half the days, and 3=nearly every day). The participant's item responses are summed to provide a total score (range of 0 to 27), with higher scores indicating greater severity of depressive symptoms. The recall period is 2 weeks.

Negative changes in PHQ-9 total score indicate improvement.

5.5.5.2. Analysis

Descriptive statistics of the actual values and the change from baseline to each postbaseline time point will be presented for PHQ-9 total score by intervention group.

Changes from baseline over time in PHQ-9 total score will be analyzed based on the same MMRM model as described for the primary endpoint with baseline PHQ-9 total score as the covariate.

Least squares mean changes from baseline (+/- SE) over time will be presented graphically.

5.5.6. Response (≥ 6 Points Improvement) Based on PHQ-9 Total Score

5.5.6.1. Definition

A participant is defined as a responder at a given time point if improvement in PHQ-9 total score is \geq 6 points at that time point.

5.5.6.2. Analysis

The number and percentage of participants who achieve response (≥ 6 points improvement) will be summarized at each time point during the double-blind phase by intervention group.

Response rates over time will be plotted for the double-blind phase.

5.5.7. Response (≥ 50% Improvement) Based on PHQ-9 Total Score

5.5.7.1. Definition

A participant is defined as a responder at a given time point if the percent improvement from baseline in PHQ-9 total score is $\geq 50\%$ at that time point (ie, percent change $\leq -50\%$).

5.5.7.2. Analysis

The number and percentage of participants who achieve response ($\geq 50\%$ Reduction) will be summarized at each time point during the double-blind phase by intervention group.

Response rates over time will be plotted for the double-blind phase.

5.5.8. Remission (PHQ-9 <5) Based on PHQ-9 Total Score

5.5.8.1. Definition

A participant is defined as a remitter at a given time point if the PHQ-9 total score is <5 at that time point.

5.5.8.2. Analysis

The number and percentage of participants who achieve remission (PHQ-9 < 5) will be summarized at each time point during the double-blind phase by intervention group.

Remission rates over time will be plotted for the double-blind phase.

5.5.9. Efficacy Data in the Double-blind Phase for Participants Who Do Not Meet Nonresponse Criteria (Randomization List 2 Analysis Set)

These summaries will be provided for the randomization list 2 analysis set. Descriptive statistics of the actual values and the change from baseline to each post baseline time point in the double-blind phase, will be presented for MADRS total score, CGI-S score and PHQ-9 score by intervention group.

Means and mean changes from baseline (+/- SE) over time will be presented graphically for MADRS total score during double-blind phase.

The number and percentage of participants who achieve remission based on MADRS total score, achieve response based on MARDS total score or achieve response based on PHQ-9 will be summarized at each time point during the double-blind phase by intervention group.

A frequency distribution over time of the CGI-S scores will be provided for the double-blind phase by intervention group.

5.5.10. Efficacy Data in the Open-Label Treatment or Observation Phase

The summaries will be provided for the open-label analysis set and observation analysis set, separately. Descriptive statistics of the actual values and the change from baseline to each post baseline time point in the double-blind and open-label treatment or observation phase, will be presented for MADRS total score and CGI-S score.

Means and mean changes from baseline (+/- SE) over time will be presented graphically for MADRS total score during double-blind phase and open-label treatment or observation phase.

The number and percentage of participants who achieve remission based on MADRS total score, achieve response based on MARDS total score will be summarized at each time point during the double-blind phase and open-label treatment or observation phase by intervention group.

Remission and response rates based on MARDS total score will be plotted for the double-blind phase and open-label treatment or observation phase.

A frequency distribution over time of the CGI-S scores will be provided for the double-blind phase and open-label treatment or observation phase by intervention group.

5.5.11. Subgroup Analyses

Forest plots will be provided displaying analysis results for each subgroup listed in Section 5.7.1. The point estimate of the treatment difference and its 95% confidence interval for each subgroup will be based on an MMRM analysis for the primary endpoint using the appropriate contrast. The model will include factors for treatment, analysis center, antidepressant treatment status at screening entry, day, subgroup, day-by-treatment interaction, treatment-by-subgroup interaction, day-by-treatment-by-subgroup, and baseline MADRS total score as a covariate. The terms in the models will be adjusted for the subgroup of baseline MADRS total score (\leq /> median). Baseline MADRS total score (as a continuous covariate) will not be included in the model when the dichotomized baseline MADRS total score is included in the model.

The analyses will be performed for the full efficacy analysis set.

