1.2. Study Design

This is a randomized, double-blind, placebo-controlled, multicenter study in male and female participants with TRD to evaluate the efficacy, safety, and tolerability of esketamine nasal spray, 56 mg and 84 mg, administered as monotherapy.

This study has 4 phases: screening, double-blind treatment, open-label treatment/observation, and follow-up.

A target of approximately 446 participants will be randomized in a 2:1:1 ratio to placebo, esketamine 56 mg, or esketamine 84 mg. A minimum of 356 participants meeting predefined nonresponse criteria will be randomized for the primary efficacy analysis set. Two separate randomization lists will be generated, a list for those participants who meet the predefined nonresponse criteria and a list for those participants do not meet the nonresponse criteria. The randomization will be stratified by study site and antidepressant treatment status (on- or off-treatment) at screening entry.

The maximum duration of study participation is 24 weeks.

Screening Phase (up to 7 weeks)

All participants will have a minimum of 2 weeks in the Screening Phase without any antidepressant (AD) medication(s) just prior to randomization.

For participants not taking any AD medication at study entry (screening), the mandatory 2-week antidepressant-free period may start at entry. However, the screening phase will be at least 3 weeks to ensure required procedures are completed.

Participants meeting the inclusion/exclusion criteria are eligible to proceed to the double-blind treatment phase.

Double-blind Treatment Phase (4 weeks)

Eligible participants will be randomly assigned at a 2:1:1 ratio to receive double-blind nasal spray treatment with either placebo, esketamine 56 mg, or esketamine 84 mg, twice a week for 4 weeks.

The participant will self-administer nasal spray treatment (esketamine or placebo) under the direct supervision of a healthcare provider during a treatment session at all treatment visits. A treatment session consists of nasal administration of the study medication and post-administration observation.

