3. SAMPLE SIZE DETERMINATION

The sample size is calculated for the full efficacy analysis set, which includes all randomized patients who meet predefined nonresponse criteria (based on MADRS assessments performed during the screening phase). A standardized treatment effect for the primary endpoint at Day 28 compared to the placebo arm of 0.45 (a treatment difference of 5.4 points for the change from baseline [Day 1 prerandomization] in MADRS total score with a standard deviation of 12) and the Hochberg procedure, with the truncation parameter equal to 1 (which results in the conventional Hochberg method with respect to the primary endpoint) to control the overall familywise error rate of 0.05 (two-sided) were used for the calculation. A 2:1:1 randomization scheme requires 71 participants per active treatment arm and 142 for the placebo arm to complete 4 weeks of treatment to achieve 85% power for each dose and 93% power to correctly reject at least one null hypothesis. Taking into consideration a 20% drop-out rate, 356 patients who meet the predefined nonresponse criteria (based on MADRS assessments performed during the screening phase) will need to be randomized in the study. The treatment discontinuation rate will be closely monitored in a blinded fashion throughout the trial.

Non-response at the end of the screening phase is based on improvement in the Montgomery-Asberg Depression Rating Scale (MADRS) total score from Week 1 to Day 1 and the MADRS total score on select screening MADRS assessments

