5.3.2.1. Analysis Methods

5.3.2.1.1. Primary Analysis

Descriptive statistics of the actual values and the change from baseline to each postbaseline time point in the double-blind phase will be presented for MADRS total score by intervention group.

MADRS total score will be analyzed by a Mixed-Effect Model for Repeated Measures (MMRM) based on observed case data. The fixed terms included in the model will be intervention group, analysis center, antidepressant treatment status (on- or off-treatment) at screening entry, day, and day-by-intervention interaction, and the baseline MADRS total score as a covariate. The within-subject covariance between visits will be estimated via an unstructured variance-covariance matrix. In case of convergence problems, alternative variance-covariance structures will be tried in the following order, with the first structure that converges being used in the analysis: heterogeneous Toeplitz, standard Toeplitz, and AR(1) with separate subject random effect. In the case that a structured covariance needs to be used, a robust sandwich variance estimator of heterogeneous Toeplitz, standard Toeplitz, and AR(1) will be used to address the potential adverse impact of covariance matrix mis-specification on the estimation and testing of treatment effect. Comparison between each dose of esketamine nasal spray and placebo nasal spray at Day 28 will be performed using the appropriate contrast. Difference in least square means and 2-sided 95% CI will be presented for each dose level.

Means and mean changes from baseline (+/- SE), and least squares mean changes from baseline (+/- SE) over time will be presented graphically.

Model Diagnostics

The normality and equal variance assumptions underlying the primary MMRM model will be assessed graphically for the MADRS total score at Day 28. Residuals from the primary models will be plotted against the predicted values and a QQ plot of the residuals versus the expected quantiles of the standard normal distribution will be presented. If either the equal variance or the normality assumption appears to be grossly violated, other methods including an ANCOVA on ranks model or an appropriate transformation of the primary endpoint might be considered.

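### The baseline-severity subgroup rows drop continuous baseline MADRS and so give up a little precision that could be kept at no cost

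*SAP*

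**What the plan says.** The primary MMRM (SAP 5.3.2.1.1) includes "day-by-intervention interaction, and the baseline MADRS total score as a covariate". The subgroup MMRM (SAP 5.5.11) adds the subgroup factor and its interactions to that model and keeps the same covariate: its list of terms ends with "day-by-treatment-by-subgroup, and baseline MADRS total score as a covariate".

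One subgroup is treated differently. SAP 5.7.1 lists baseline MADRS split at its median. For that subgroup, 5.5.11 first says that the model terms will be adjusted, and then: "Baseline MADRS total score (as a continuous covariate) will not be included in the model when the dichotomized baseline MADRS total score is included". It gives no reason, and no other section restores an adjustment for baseline score within the two halves.

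The output is descriptive. On the forest plots, "The point estimate of the treatment difference and its 95% confidence interval for each subgroup will be based on an MMRM analysis"; no test and no share of alpha is attached. On allocation, SAP 1.2 states: "The randomization will be stratified by study site and antidepressant treatment status (on- or off-treatment) at screening entry". Baseline MADRS is not a stratification factor.

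**The concern.** A two-level indicator discards what is known about a participant's baseline score beyond which side of the median it falls on. Participants within one half still differ in severity, and the arms within that half are balanced on severity only in expectation. The primary model and the other subgroup rows use the continuous score to remove this source of noise; the severity rows do not.

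Nothing forces the choice. The median split and the continuous score are correlated, but they are not redundant. The split and its interactions carry the subgroup comparison, while the continuous term absorbs the remaining variation in baseline. The correlation makes the subgroup main effect less precise, but that effect is not plotted. The plotted quantities are treatment contrasts within each half, and these do not suffer.

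What is at stake is the width of the intervals in a few descriptive rows, for a subgroup that readers are likely to look at.

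**Working it through.** **Inputs from the documents.** The sample size section (SAP 3) assumes "a treatment difference of 5.4 points for the change from baseline [Day 1 prerandomization] in MADRS total score with a standard deviation of 12", 2:1:1 allocation, 142 placebo and 71 per active arm completing, and 20% dropout.

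**The plan's own figures.** A normal-theory simulation of the Hochberg procedure with a shared placebo arm (142/71/71) gives 85.9% power per dose and 93.9% for at least one dose, against the stated 85% and 93%. Dropout: 142/0.8 = 177.5, rounded up to 178; 71/0.8 = 88.75, rounded up to 89; 178 + 89 + 89 = 356, as stated. The SAP gives no figure for the subgroup analysis.

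**Inputs that have to be assumed.** The documents give neither the correlation *r* between baseline MADRS and the Day 28 change nor the SD of baseline MADRS. I take *r* from 0.2 to 0.5 and an approximately normal baseline.

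**Step 1: what the split retains.** For a normal variable, a median split explains 2/π = 0.637 of the variance. The remaining 36% lies within the halves, where the SD is √(1 − 2/π) = 0.603 of the overall SD.

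**Step 2: standard error of one dose contrast within one half.** With all 356 randomised, a half holds about 89 placebo and 44.5 participants per dose, and √(1/89 + 1/44.5) = 0.1836. With outcome SD 12, the unadjusted standard error is 12 × 0.1836 = 2.20 points.

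- Split only: 2.20 × √(1 − 0.637*r*²)
- Split plus continuous baseline: 2.20 × √(1 − *r*²)
- Ratio: √[(1 − 0.637*r*²)/(1 − *r*²)]
- SD of the difference between the two estimates: *r* × 12 × 0.603 × 0.1836

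| *r* | SE, split only | SE, with continuous baseline | Ratio | SD of shift (points) |
|---|---|---|---|---|
| 0.2 | 2.17 | 2.16 | 1.008 | 0.27 |
| 0.3 | 2.14 | 2.10 | 1.018 | 0.40 |
| 0.4 | 2.09 | 2.02 | 1.034 | 0.53 |
| 0.5 | 2.02 | 1.91 | 1.059 | 0.66 |

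A single-visit simulation (356 participants, 2:1:1, 4,000 runs) puts the SD of the shift at 0.30, 0.42, 0.55 and 0.67 points. That is slightly above the closed form because the slope has to be estimated.

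**Step 3: the last two columns are one effect.** At *r* = 0.5, √(1.91² + 0.66²) = 2.02, the split-only standard error, and 2.02/1.91 = 1.06. The shift is the extra variance, and the split-only confidence interval already contains it.

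**Step 4: cross-check with other assumptions.** This run used 142/71/71 completers, baseline SD 4 to 8 and a slope of change on baseline of 0.25 to 1.0. The implied *r* is slope × baseline SD/12, that is 0.25 × 4/12 = 0.08 up to 1.0 × 8/12 = 0.67. The mean half-specific estimate stays at about −5.4 with or without the continuous term. The SD of the shift runs from 0.2 to 1.0 points. At baseline SD 6 and slope 0.5 (*r* = 0.25), the empirical standard error goes from 2.36 without the continuous term to 2.34 with it. At the extreme corner (*r* = 0.67) it goes from 2.11 to 1.87.

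**The case against.** The strongest reply is that this is a deliberate, prespecified choice. Replacing a continuous covariate with its own categorised form, when that form is the subgroup factor, is an acceptable specification, and nothing in the documents requires the continuous term to stay. The rows are unpowered estimates with intervals for one of seven listed subgroups. Most of this stands. The plan does not contradict itself here; it simply leaves some precision unused.

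The reply is also right about three stronger readings that a reader might take from the sentence:

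- **That the severity rows are biased.** They are not. Arms are randomised, so the contrast within each half has the same expectation with or without the covariate, and the simulated means agree.
- **That wider intervals and sensitivity to chance imbalance are two separate harms.** Step 3 shows that they are the same variance.
- **That the rows cannot be compared with the rest of the plot.** In a linear model with randomised arms, the adjusted and less adjusted contrasts estimate the same mean difference. An interval a few percent wider does not change that.

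A further caveat concerns the formula, which is for a single visit. The SAP's MMRM has no baseline-by-day term, so continuous baseline has one slope shared across Days 2 to 28. Where the Day 28 slope differs from the shared one, the gain at Day 28 would be smaller than the table shows.

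What does not stand is the inference that nothing should change. The loss is small but real, and avoiding it has no statistical cost.

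**Conclusion.** The point holds as a minor and avoidable loss of precision. For the baseline-severity rows alone, the standard error of a half-specific dose contrast is about 1% to 6% wider than it need be. Equivalently, the estimate moves at random with an SD of about 0.3 to 0.7 points, against a row standard error of about 2 points and a planned effect of 5.4. These sizes rest on an assumed correlation of 0.2 to 0.5, a roughly normal baseline, all 356 participants contributing, and the single-visit approximation. A correlation outside that range would move them, as Step 4 shows. The absence of bias follows from randomisation; with dropout it also relies on data being missing at random given the model terms.

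A reader might suppose that the main results are touched. They are not. The primary model keeps "the baseline MADRS total score as a covariate", the key secondary analysis uses that same model, and the multiplicity procedure in SAP 5.3 covers only the Day 28 and Day 2 dose comparisons.

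**What to change.** In SAP 5.5.11, delete the sentence that removes the continuous covariate. State instead that continuous baseline MADRS stays in the model beside the median-split factor and its interactions. Reword the preceding sentence, which says that the terms will be adjusted for this subgroup, so that the two agree. If the sponsor prefers to keep the planned model, reporting the version with the continuous covariate as a check would be enough.

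The cost is two sentences of SAP text and one model statement. It needs no new data, alpha or output. This is a free improvement of the lowest priority.
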